## 5. Inclusion/Exclusion Criteria

Inclusion criteria	Exclusion criteria

 
• age 65 years or older
 
• able to read and write English
 
• cLBP that has persisted at least 3 months and pain on at least half of the days for the previous 6 months
 
• average intensity of pain <math>\geq 4</math> on a 11-point numerical pain scale in the previous week
 
• have intact cognition (Mini-Mental State Examination, MMSE <math>> 24</math>)
 
• willing to commit to 4-weekly study visits and up to 12-months follow-up.
 
• able to apply pressure to the seeds with tapes on their ears
 
	
 
• malignant or autoimmune diseases (e.g., rheumatoid arthritis)
 
• known acute compression fractures caused by osteoporosis, spinal stenosis, spondylolysis, or spondylolisthesis because these conditions may confound treatment effects or the interpretation of results
 
• sciatica with leg pain greater than back pain
 
• allergy to the tape
 
• use of some types of hearing aids (size may obstruct the placement of seeds)
 
• pain in other parts of the body that is more severe than the cLBP and which occurs daily or almost every day with at least moderate intensity or acute pain; neurological disorders that could interfere with pain reporting or confound performance on the other outcomes, cerebral tumor, Alzheimer's disease (or other cognitive illnesses), prior stroke, or multiple sclerosis
 

## 6. Drugs/ Substances/ Devices

N/A

## 7. Study Statistics

### a. Primary outcome variable.

Adherence to APA practice, medication use, and real-time cLBP measurement of HRQoL, satisfaction, treatment beliefs and expectations, sleep, relaxation effects, catastrophizing and fear/avoidance.

### b. Secondary outcome variables.

The serum levels of IL-1 $\alpha$ , IL-1 $\beta$ , IL-2, IL-4, IL-6, IL-8, IL-10, IL-12, IL-13, IL-17, IFN- $\gamma$ , TNF- $\alpha$ , CGRP, and TGF- $\beta$

### c. Statistical plan including sample size justification and interim data analysis.

The primary outcomes are measured at 1-month post-completion of treatment. In our pilot study (i.e., pain intensity, pain interference, and physical function), Cohen's d (the effect sizes in terms of the standardized difference) ranged from 0.65 (physical function) to 1.28 (pain intensity) between the APA and the sham APA one month after intervention. Our pilot sham group (CG 1, non-reactive points) should have similar or better outcomes than CG 2 (enhanced usual care). The power calculation is based on the smallest observed effect size of 0.65 for a more conservative estimate for the sample size required in this proposed study to detect a difference between the active intervention and either of the control conditions. With 150 participants (50 participants in each of the three groups), we will be able to achieve 90% power to detect an effect size of .65 (between the APA and either of the CG arms) at a two-tailed significance level of 0.05. We anticipate that approximately 10% will be lost to follow-up at 1-month (primary endpoint) based on our pilot study (10% dropout at 1-month follow-up after 4-week APA), and [name] R01 (11% after 5 months follow-up). We plan to recruit 200 participants to allow for an adequate sample size in our exploratory analysis of the 12-month follow-up, assuming 25% of the enrolled sample will be lost to follow-up at 12-months. Achieving this sample size during a 42-months accrual period will require enrolling 58 participants per year, which should be feasible through our proposed recruitment strategies. With this sample size, we will be able to detect significant changes in some of the biomarkers (CGRP) but not all based on our pilot studies. We are collecting these to get a better estimate of the effect using a larger sample size.

Analysis plan for aim 1 will be to determine the efficacy of APA for cLBP at one month post treatment. For continuous outcomes, we will use a general linear mixed model (GLM) to construct a multilevel model for comparing the differences in the change in the outcomes from baseline to one month among the three groups. The group-by-time interaction is the main parameter of interest. This model will adjust for fixed

effects from important demographic and clinical covariates, if needed. Random effects from subject heterogeneity and temporal autocorrelation with the first-order autoregressive (AR(1)) covariance structure will be used to model the repeated measurements. The comparison of all outcome measures between, before, and after APA will assess possible treatment placebos (i.e., point specificity) and blindness of intervention. In addition to reporting mean score changes of outcomes reaching clinical significance, a cut point of 30% improvement for primary outcomes will be used for responder analysis. For responder analysis of primary outcomes, we will adopt a generalized logistic mixed model with the same fixed and random effects and AR(1) covariance structure. In both models, violation of assumptions will be detected by corresponding model diagnostics. Using the approach outlined above, analyses will be conducted using the monthly data through 12 months to explore the maintenance of the effect over time. Quadratic terms will be included in the model to allow for non-linear change across time.

Analysis for aim two, evaluating the effect of APA on biomarkers, the analytical strategies for Specific Aim 1 will be used. Outcomes at one-month post treatment will be examined using each biomarker individually and two latent variables with pre-defined biomarkers within the groups of pro- and anti-inflammatory biomarkers. We hypothesize that the analgesic effects of APA are the aggregating and counter-interacting effects of different biomarkers within each latent variable. Before analysis, we will check the normality assumption in original data and log-transformed data. If normality cannot be met in both types of data, we will use two alternative approaches: we will apply a non-parametric test (e.g., Kruskal-Wallis test) to do multiple comparisons in each time difference among three groups; We will categorize the change of biomarker measurement into increase (recoded as 1) and decrease (recoded as 0) from baseline, and apply a GLM, which can handle repeated measurements and subject heterogeneity. To examine the sustained effect of the intervention over time in biomarkers (baseline, 1, 3, 6, 9, 12 months), we will use the approach described in Aim 1 using linear mixed models with quadratic terms to model the change in biomarkers across time. Each biomarker will be tested individually and the two latent variable within pro- and anti-inflammatory biomarkers as well.

Aim three analyses will examine the moderating effects of demographics, comorbid conditions, treatment, and placebo effects, as well as the mediating effects of biomarkers in both primary and secondary outcomes. To examine whether or not demographics, comorbid conditions, and placebo effects moderate the relationship between APA treatment on primary and secondary outcomes, the previously described regression models in Specific Aim 1, which include the main effect terms for the intervention or group, will be

expanded to include the main effect terms for moderators and the three-way interaction terms between group, time, and moderators. Models will be simultaneously estimated under a framework of a mixed model structure by adding a covariance structure to consider possible correlations among biomarkers.

Appropriate model statistics (e.g., estimated regression coefficients [with 95% confidence intervals] for the interaction terms, change statistics based on likelihood ratio test, and F-statistics) will be used to evaluate moderation effects. Latent variable models will be used to examine the mediation effect of inflammatory biomarkers. Group assignment will be the independent variable and change in outcome from baseline to 1-month post treatment will be the dependent variable. Change in inflammatory biomarkers from baseline to immediately post-intervention will be included in the model as a mediator. The parameter of interest will be the indirect effect of treatment group through inflammatory biomarkers on change in outcomes.

d. Early stopping rules.

We do not expect any adverse events related to the testing procedures as they have no remarkable health risks. However, we will report all adverse events and evaluate on a case-by-case basis whether the occurrence of a particular adverse event has implications for discontinuing the study to ensure participant safety and well-being. Patients are allowed to drop out from the study if they do not feel comfortable with the procedures or they have an allergic reaction to the tape used for APA.

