**Evidence supporting the use of auricular acupressure and acupuncture for chronic pain shows promise but larger studies that address methodological issues are needed.** Studies of auricular acupressure or acupuncture have demonstrated promising efficacy for pain management. We conducted pilot studies in APA: (1) individuals with chronic low back pain (cLBP), (2) breast cancer (BC) patients with persistent post-mastectomy pain, and (3) postmenopausal breast cancer survivors with aromatase inhibitor arthralgia (AIA). All of our pilot studies demonstrated better than a clinically significant difference of pain reduction (defined as a 30% reduction) after 4 weeks of APA (Table 1) and sustained effects for 1-month follow-up. Our pilot data also show blood-level reduction in pro-inflammatory cytokines (e.g., IL- $\beta$ ) and calcitonin gene-related peptide (CGRP), and increased anti-inflammatory cytokines (e.g., IL-4) suggest APA impacts neural-immune signaling. A meta-analysis (17 studies including three conducted in the U.S.) found evidence that auricular acupuncture reduces analgesic use in perioperative settings as well as other forms of acute and chronic pain. In our meta-analysis of 13 studies of auricular acupressure and acupuncture for pain management, auricular acupressure and acupuncture provided significant pain reduction compared to sham or control groups (standardized mean difference [SMD] of -1.59, 806 participants across 13 trials). Among four APA studies (275 participants) included in the meta-analysis, we observed a large effect size of APA, with a standardized mean difference of -1.85, indicating that the mean decrease in pain score for APA was on average 1.85 standard deviations greater than that in the sham control. Evidence supporting APA remains limited: few studies were RCTs (only 4 APA were included in the meta-analysis), sample sizes tended to be small, short-term follow-up, blinding procedures were inadequate, and several studies lacked sham group comparisons. *Additionally, we cannot assume the beneficial effects of body or auricular acupuncture for pain relief will simply translate to APA because the stimulation between needle and acupressure may differ.* Evidence points to several potential biological mechanisms of action for APA. Neurophysiological connections between ear points and the human central nervous system have been supported by fMRI. Similar to acupuncture, APA can change autonomic function, including heart rate and heart rate variability. We have gathered preliminary data that support the existence of a neural immune pathway that interrelates the ear microsystem and somatotopic brain areas (i.e., decreased pro-inflammatory cytokines [IL- $\beta$ , IL-2, IL-6] and increased anti-inflammatory cytokines [IL-4] in serum) in patients with chronic low back pain, suggesting that APA impacts neuro-immune signaling.

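### The Aim 1 three-group mixed model makes no provision for variance to differ by arm, although the cLBP pilot's SDs of pain change (2.66 with APA, 1.41 with sham) suggest that it may

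*Combined protocol and SAP*

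**What the plan says.** Section 7c sets out how Aim 1 outcomes on a continuous scale are to be analysed: "we will use a general linear mixed model (GLM) to construct a multilevel model for comparing the differences in the change in the outcomes". The comparison covers all three groups, baseline against one month post treatment. "The group-by-time interaction is the main parameter of interest". Subject heterogeneity is handled by random effects, and "temporal autocorrelation with the first-order autoregressive (AR(1)) covariance structure will be used to model the repeated measurements".

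On assumptions, the plan says only this: "In both models, violation of assumptions will be detected by corresponding model diagnostics". No action is named for Aim 1 if a diagnostic fails. Aim 2, by contrast, names fallbacks, though only for non-normal biomarkers. Nothing in Section 7c mentions arm-specific variances, robust standard errors or a degrees-of-freedom method.

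The relevant pilot data are in Section 3, Table 1. They are mean changes in pain intensity with SDs, for APA and sham, in three pilots. The accompanying text dates the main results "after 4 weeks of APA (Table 1) and sustained effects for 1-month follow-up".

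**The concern.** Pain intensity is one of the three primary outcomes in Section 2 (Hypothesis a). The only cLBP data in the documents on the spread of its change show far more spread with APA than with sham.

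A random subject intercept cancels out of a within-person change. With a common AR(1) residual, the model therefore implies the same variance of change in every arm, 2 × sigma² × (1 − rho) at the given lag. In a two-arm trial with equal arms this does little harm, because the pooled variance is the average of the two variances that enter the contrast. In a three-arm trial the third arm enters the pooled variance but not the contrast, so the standard error can be wrong even at 1:1:1.

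At stake are the confidence intervals and p-values for APA against each control. The plan would detect unequal variances but does not say what would then be done.

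**Working it through.** **Plan's own figure.** "The power calculation is based on the smallest observed effect size of 0.65", and 50 per arm is said to give 90% power, two-sided 0.05. Check: n = 2 × (1.96 + 1.2816)² / 0.65² = 49.7, so 50 per arm; power at 50 is 0.901 (0.896 with the noncentral t). Enrolment: 150 / 0.75 = 200. Both reproduce. Expected at the primary endpoint: 200/3 × 0.9 = 60 per arm.

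**Inputs**
- cLBP pilot (n=61): SD of change 2.66 (APA) and 1.41 (sham). Variances 7.0756 and 1.9881; ratio 3.56.
- Breast cancer pilot (n=31): 2.62 and 2.96; ratio 0.78.
- Aromatase inhibitor arthralgia pilot (n=20): 0.96 and 0.82; ratio 1.37.
- Allocation 1:1:1 (Section 4, Randomization).
- SD of change in CG-2: not given. Assumed range 1.41 (as sham) to 2.66 (as APA).

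**How firm is 3.56?** The split of the 61 is not given. Assuming 30/31, the F test gives two-sided p of about 0.0009; assuming 37/24, 0.0021. Under 30/31 and normality, the 95% interval for the ratio is about 1.7 to 7.4.

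**Effect of one common variance**

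V_pool = (V_APA + V_CG1 + V_CG2) / 3

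Model SE / true SE = sqrt(2 × V_pool / (V_APA + V_CG))

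Coverage = 1 − 2 × (1 − Phi(1.96 × ratio))

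- CG-2 SD 1.41: V_pool = (7.0756 + 1.9881 + 1.9881)/3 = 3.684. Both contrasts: sqrt(7.368/9.064) = 0.902.
- CG-2 SD 2.66: V_pool = (7.0756 + 1.9881 + 7.0756)/3 = 5.380. APA vs CG-1: sqrt(10.760/9.064) = 1.090. APA vs CG-2: sqrt(10.760/14.151) = 0.872.
- CG-2 SD 2.035 (midpoint): V_pool = (7.0756 + 1.9881 + 4.1412)/3 = 4.402. APA vs CG-1: 0.986. APA vs CG-2: 0.886.

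| CG-2 SD (assumed) | Contrast | SE ratio | Coverage | Simulated two-sided error, 50 / 60 per arm |
|---|---|---|---|---|
| 1.41 | APA vs CG-1 | 0.902 | 92.3% | 7.8% / 7.9% |
| 1.41 | APA vs CG-2 | 0.902 | 92.3% | 7.8% / 7.7% |
| 2.035 | APA vs CG-1 | 0.986 | 94.7% | 5.4% / 5.3% |
| 2.035 | APA vs CG-2 | 0.886 | 91.8% | 8.1% / 8.1% |
| 2.66 | APA vs CG-1 | 1.090 | 96.7% | 3.3% / 3.3% |
| 2.66 | APA vs CG-2 | 0.872 | 91.3% | 8.7% / 8.9% |

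The simulations used 100,000 sets of change scores per row. As a check on the reduction to change scores, 400 random-intercept mixed models (two time points, 60 per arm, CG-2 SD 1.41) gave 7.3% and 8.3%, with Monte Carlo error of about 1.3 points.

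**Comparators**
- Arm-specific variances: error 4.9% to 5.1% in every cLBP row.
- Two-arm pooled variance, equal arms: 4.9% to 5.1%.
- Three-arm pooling with the other pilots' SDs (CG-2 as sham): 4.5% to 4.6% (breast cancer), 5.5% to 5.7% (arthralgia).
- Omnibus three-group test with the cLBP SDs: 5.4% to 5.9%. The distortion falls mainly on the pairwise contrasts, and it is these that the power statement addresses.

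**The case against.** The strongest reply is that the plan never says the variance is common to the arms. That is correct. It is what such a model gives by default, and diagnostics are promised. A reader might infer that the plan has chosen a single variance and that the primary p-values are therefore wrong; the text supports neither. What stands is that the plan is silent, and that "violation of assumptions will be detected by corresponding model diagnostics" names no remedy.

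The evidence is also thin. It is one pilot, for pain intensity only, after 4 weeks of APA rather than one month after treatment ended. No SDs of change are reported for pain interference, physical function or CG-2. The other two pilots do not show the pattern, though they are smaller and in other conditions. At the lower limit of 1.7 for the ratio, with CG-2 like sham, the actual error would be only about 6.1%. All of this stands and makes the size conditional.

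The error rates above 5% assume equal means together with a large variance gap. In the pilot, that gap came with a large mean difference (-3.53 against -0.77), which would fit varied response to an effective treatment. Coverage is therefore the better measure, and the shortfall from 95% is at most 3.7 points over the range examined.

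A sample-size paragraph in Section 4 (under Study Site) refers to a two-group repeated-measures model, in which the problem nearly vanishes at equal arm sizes. But that is sample-size text, and the Aim 1 analysis in Section 7c is explicitly three-group.

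Finally, residual variances can be inspected without looking at the treatment contrast, so a later remedy need not be driven by the result. That is fair; pre-specification simply removes the question.

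**Conclusion.** The point holds as a conditional one. The Aim 1 model makes no provision for variance to differ by arm, and the sponsor's own cLBP pilot gives reason to expect that it might. If the ratio of 3.56 recurs and a common covariance is fitted, standard errors for the APA contrasts run from about 13% too small to about 9% too large, with coverage from about 91.3% to 96.7%. The size and direction depend on the CG-2 SD, which the documents do not give. Nothing makes 1.41 the likely value: Section 7c expects sham to have similar or better outcomes than CG-2, which says nothing about spread.

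The calculation rests on change from baseline to one month, equal arms and approximate normality; extra time points were not modelled.

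Two wider readings are not supported. A reader might extend the point to the biomarker models, but no biomarker SDs are reported, so no claim is made there. A reader might also infer that the sample size is wrong, but it rests on a standardised effect and reproduces. This is a cheap improvement, held with moderate confidence.

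**What to change.** Add to the Aim 1 analysis of continuous outcomes in Section 7c: residual covariance will be estimated separately by arm (in SAS, for example, REPEATED with GROUP=arm), with Kenward-Roger or Satterthwaite degrees of freedom, and APA vs CG-1 and APA vs CG-2 will be estimated from that model.

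The cost is one sentence and a few variance parameters: with AR(1), a variance and a correlation in each of three arms, so six instead of two. Intervals may widen or narrow with the arm SDs. At the cLBP pilot SDs:
- CG-2 SD 1.41: both contrasts about 11% wider (1/0.902 = 1.109).
- CG-2 SD 2.66: APA vs CG-2 about 15% wider (1/0.872 = 1.147), APA vs CG-1 about 8% narrower (1/1.090 = 0.917).

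If the arms turn out to have equal variances, little precision is lost. No change to the sample size is needed.

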Our team's pilot data shows that using APA in older adults with cLBP resulted in 40% less pain one day after starting APA. We found that a four-week treatment achieves even greater pain relief (44% reduction) as well as improved function, both of which are maintained at the one-month follow-up. Blood-level reduction in pro-inflammatory cytokines (e.g., IL-β) and calcitonin gene-related peptide (CGRP) and increased anti-inflammatory cytokines (e.g., IL-4) suggest APA impacts neural-immune signaling. Further, we have developed and piloted a smartphone application (app) of ecological momentary assessment (EMA) to collect real-time cLBP outcomes associated with APA, with good usability reported by patients, which limits recall bias. Pilot data combined with the feasibility of implementing APA widely in clinical practice provide the impetus for pursuing the next stage of research—evaluating the sustained efficacy of APA for cLBP.

We propose a randomized controlled trial to: (1) determine the efficacy of APA in relieving cLBP, and (2) examine the physiological impact of APA on cLBP in 200 adults 65 years or older (n=200 will be able to provide 90% power to detect 30% function improvement). To address possible placebo effects of treatment (i.e., point specificity) and nonspecific psychological factors (i.e., treatment beliefs, expectations, and patient-provider relationship), we will use a three-group design: (1) APA (active ear points relative to cLBP), (2) Comparison Group (CG)-1 (non-active points, not related to cLBP), (3) CG-2 (enhanced educational control). Our EMA app will be used to monitor APA adherence and capture daily momentary cLBP outcomes and analgesic use. Outcomes will be measured via EMA, weekly during intervention, 1-month after completion of APA (primary endpoint), and monthly follow-up up to 12-months to assess sustained effects. Our approach addresses the mission of the National Institute on Aging, the standardized research approach on cLBP suggested by the NIH Pain Consortium Research

PROTOCOL NUMBER: 21-1059

IRB APPROVAL DATE: 02/04/2022

Task Force and the Surgeon General's challenge to limit prescription of opioids by providing a nonpharmacological strategy.

2. Objectives (include all primary and secondary objectives)

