- **Specific Aim 1.** Determine the efficacy of APA for relieving cLBP at 1-month after completion of APA (primary endpoint) and explore monthly follow-up to 12-months to assess sustained effects of APA.

**Hypothesis a:** the APA group will experience significant improvement in cLBP primary outcomes (i.e., pain intensity, pain interference, and physical function) compared to the CGs. **Hypothesis b:** the APA group will experience significant improvement in cLBP secondary outcomes (i.e., lower analgesic use [the use of over-the-counter and prescription analgesics including opioids], quality of life, satisfaction, anxiety, depression, fear/avoidance, catastrophizing, improved relaxation, and sleep) compared to the CGs.

- **Specific Aim 2.** Determine the effects of APA on inflammatory signaling in cLBP. **Hypothesis:** APA will decrease circulating pro-inflammatory biomarkers (i.e., IL-1 $\beta$ , CGRP) and increase anti-inflammatory cytokines (i.e., IL-4) compared to the CGs.

- **Specific Aim 3.** Examine the relationship among potential mediators and moderators influence beneficial effects of APA on cLBP. **Hypothesis:** APA-induced cLBP symptom reduction will be mediated by changes in circulating inflammatory biomarkers and moderated by nonspecific placebo effects, relevant biological variables (e.g., age, gender, BMI), ethnicity, marital status, and comorbid conditions (e.g., smoking).

3. Background (briefly describe pre-clinical and clinical data, current experience with procedures, drug or device, and any other relevant information to justify the research)

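### The main test is a three-group interaction on three unranked primary outcomes, with no rule on which contrast or how many outcomes must succeed; a significant result would not show that APA beats sham

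*Combined protocol and SAP*

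**What the plan says.** Objectives, Specific Aim 1, Hypothesis a, predicts improvement in "cLBP primary outcomes (i.e., pain intensity, pain interference, and physical function) compared to the CGs". Table 4 lists the same three outcomes as primary, without ranking them.

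Section 7c compares the change from baseline to one month across the three groups with a mixed model and states: "The group-by-time interaction is the main parameter of interest". It then adds that comparisons of the outcome measures "will assess possible treatment placebos (i.e., point specificity") and blinding, but gives no contrast, order or criterion.

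The sample-size text of the same section is pairwise: with 50 per group "we will be able to achieve 90% power to detect an effect size of .65 (between the APA and either of the CG arms"), with alpha 0.05 two-sided. The other sample-size text, in Section 4, also uses a two-group model of APA against either control. Section 7c expects that the sham group "should have similar or better outcomes than CG 2".

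The Abstract gives the reason for three groups: "To address possible placebo effects of treatment (i.e., point specificity"), together with nonspecific psychological factors.

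The 0.05 level appears only in the sample-size texts. No section gives an alpha adjustment, a lead outcome, a testing order, or a rule on whether APA must beat CG-1, CG-2 or both. The only mention of multiple comparisons is in the non-parametric fallback for biomarkers in Aim 2.

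**The concern.** The named test and the question do not match. A 2-df interaction asks whether the three groups differ in any way. It can be significant because both ear-seed groups differ from education while APA and sham are the same, and that is the pattern the sham arm was included to detect.

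The trial is also sized for one contrast on one outcome, while the analysis offers three outcomes and two controls. With no written rule, the basis for an efficacy claim could be chosen after the results are known: any outcome or all three, and sham, education or both. The error rate and the power both depend on that choice.

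**Working it through.** **1. The plan's own figure.** Inputs from Section 7c: d = 0.65, two-sided alpha 0.05, power 90%. n = 2(1.960 + 1.282)²/0.65² = 21.02/0.4225 = 49.7, so 50 per arm. Power at 50 per arm is 90.1% by the normal formula and 89.6% by the t test. Enrolment is 150/0.75 = 200. The figures reproduce, for one pairwise contrast on one outcome.

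**2. Numbers at the primary endpoint.** Section 7c states: "We anticipate that approximately 10% will be lost to follow-up at 1-month (primary endpoint"). So 200 × 0.90/3 = 60 per arm. Section 4 gives 270 enrolled with 30% loss: 270 × 0.70/3 = 63 per arm.

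**3. The interaction when APA equals sham.** With complete data at two time points, the interaction test is an F test on change scores. Let CG-2 differ by d SD from two equal groups. The deviations from the overall mean are d/3, d/3 and -2d/3, so the noncentrality is n × (2/3)d².
- 50 per arm, d = 0.65: 50 × 0.2817 = 14.08. With F(2,147) and critical value 3.06, the test is significant in 92.4% of trials (a simulation gave 92.8%).
- 60 per arm, d = 0.65: 60 × 0.2817 = 16.90. With F(2,177) and critical value 3.05, it is significant in 96.3%.
- 50 per arm, d = 0.3 and 0.5: 32% and 73%.

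These rates are per outcome and do not depend on the correlation between outcomes. In all of them the true APA-sham difference is zero.

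**4. Three interaction tests with all groups equal.** If the outcomes are independent, 1 - 0.95³ = 14.3%. The correlation is not in the documents. By simulation, at least one test is significant in about 13% of trials at correlation 0.5 and about 9% at 0.9. These counts include any direction. All three are significant in about 0.3% at 0.5 and about 2% at 0.9.

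**5. Other rules the wording permits.** With all groups equal, the chance of at least one false result in APA's favour at correlation 0.5 (range for 0.9 to 0) is as follows; a single two-sided 0.05 test gives 2.5%.
- Pairwise contrasts only after a significant interaction: 5.4% (3.6-6.1%).
- All six contrasts at 0.05: 11% (7-13%).
- Both controls must be beaten: 1.3% (0.9-1.4%).

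**6. Power under explicit rules.** This is for physical function at d = 0.65 and correlation 0.5. It assumes the pilot's APA-versus-sham effects (0.65 function, 1.28 pain intensity) hold against both controls. Interference is set at 0.65, because the documents give no separate figure.

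| Rule | 50 per arm | 60 per arm |
|---|---|---|
| One contrast, one outcome | 90% | 94% |
| Sham contrast, Holm over three outcomes | 88% | 93% |
| Both controls, single lead outcome | 83% | 90% |
| Both controls, Holm over three outcomes | 79-80% | 88% |

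The last row at 63 per arm is about 90%. Over correlations 0.9 to 0 it is 78-81% at 50 per arm and 87-89% at 60.

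**The case against.** The strongest reply is that Hypothesis a joins the three outcomes with *and*, and that the trial is sized on the smallest of the pilot effects. If all three must succeed, there is nothing to correct (0.3% in step 4). That is right as far as it goes. It rules out saying that the outcomes go uncorrected under every reading. But no passage adopts that rule, and it would not repair the interaction, which step 3 shows can be significant without any sham effect.

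A second reply is that 13% is not the rate of false claims for APA. This also stands. It counts interactions in any direction, including those where APA is worse or only the controls differ; it needs success on any one outcome; and it rests on an assumed correlation. The 14% end requires uncorrelated outcomes, which is unlikely when Table 4 takes all three from one short instrument. A reader might take 13% as the trial's false-efficacy rate, and the documents do not support that.

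Third, the plan does intend to examine point specificity and expects sham to do at least as well as education. Both show that sham is seen as the harder comparator. Neither is a decision rule.

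Finally, a reader might infer that APA has to beat both controls. That is one defensible definition of efficacy, but the phrase about either control arm does not impose it. The sham contrast alone would answer the point-specificity question.

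**Conclusion.** The point holds. The test named as the main one cannot establish that APA beats sham, and the plan states no success rule across outcomes or controls. The first part does not rest on an assumed correlation: with APA equal to sham and both 0.65 SD better than education, about 92-96% of trials give a significant interaction per outcome at 50-60 per arm.

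The false-positive figure is conditional. It is about 13% (9-14%) in any direction if one significant interaction is enough and all groups are equal, and there is no inflation if all three outcomes must succeed. The stated 90% power applies to one contrast on one outcome, and what remains depends on the rule chosen. The size of the trial can support a valid claim; the rule needs to be written before unblinding.

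**What to change.** Replace the omnibus interaction as the primary test with the 1-month APA-versus-CG-1 contrast in change from the mixed model, and report APA versus CG-2 alongside it. State the success rule before unblinding: either one lead outcome, or Holm across the three outcomes at two-sided 0.05.

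If efficacy is to mean beating both controls, require both contrasts for an outcome, with no alpha split between them, and apply Holm to the larger of the two p-values.

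Do not combine a sham-first order within each outcome with Holm across outcomes unless the passing of alpha is fully specified. Suppose APA beats sham but equals education on two outcomes, and equals sham on the third. The two-sided family-wise error is then 8.5-8.8% if education is tested at the Holm level, and about 13.5% if it is tested at 0.05. The plan's expected ordering of the controls makes this case unlikely, but the procedure does not control error as a general rule.

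The cost is wording and a restated power, with no added enrolment. Against the stated 90% at 50 per arm, the sham contrast with Holm keeps 88% (93% at 60). Both controls with Holm falls to 79-80% (88% at 60), which is not a small loss at the plan's own 50 per arm. Both controls on one lead outcome gives 83% (90% at 60).

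As a separate point, Section 7a gives a different primary list ("Adherence to APA practice, medication use, and real-time cLBP measurement of HRQoL" and others) that contains none of the three outcomes by name. It must be reconciled with the Objectives, Table 4 and Section 7c, so that the set of primary tests is fixed.
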